2.3 Endpoints

Primary endpoint(s)

The primary endpoints of this study will be the following:

- Percentage of subjects who experience at least one treatment-emergent adverse event (TEAE)
- Percentage of subjects with abnormal and clinically significant (CS) safety laboratory test results at least once post-dose
- Percentage of subjects with abnormal and CS electrocardiogram (ECG) test results at least once post-dose
- Percentage of subjects with abnormal and CS vital sign measurements at least once post dose

Secondary endpoints(s)

- Single-dose plasma PK parameters of CVN766 including time to maximum plasma concentration (T_{max}), area under the plasma concentration-time curve from time 0 to 24 (AUC_{24}) and time 0 to infinity (AUC_{inf}), and terminal elimination half-life ($t_{1/2z}$) Multiple-dose plasma PK parameters of CVN766 including C_{min} , C_{trough} , C_{max} , AUC from time 0 to the end of dosing interval (AUC_t), terminal elimination half-life ($t_{1/2z}$), accumulation ratio (R_{acc}), time to steady-state ($T_{ss,max}$), steady-state C_{max} ($C_{max,ss}$), and steady-state C_{min} ($C_{min,ss}$) Single-dose and multiple-dose CSF concentrations and CSF: plasma ratios of CVN766

Other endpoints(s)

- Change from baseline in safety laboratory and ECG test results and vital signs.
- Additional plasma PK parameters of CVN766: CL/F or CL/F_{ss} and Vz/F or Vz/F_{ss}

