- **Concomitant Medications:** Concomitant medications are defined as any medication (other than the study drug) that was used at least once after the first administration of the study drug.

Medications that were stopped on the same date as the first study drug administration will be defined as concomitant medications. If a clear determination cannot be made (partial medication end dates) the medication will be classified as concomitant

- Treatment Emergent Adverse Events (TEAEs): are defined as adverse events that occurred within 30 days (onset date – last date of dose + 1 ≤ 30) after study drug administration.

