11.1 Adverse Events

All AEs including will be coded using latest MedDRA version. All AE summaries will be restricted to TEAEs only. AEs will be grouped by system organ class (SOC) and preferred term (PT) and summarized, by actual treatment group and overall. Summary tables will include the number of participants (%) experiencing an event and the number of events. Participants will be counted only once for each SOC and PT level; they will be sorted alphabetically and for PT tables only, they will be ordered with the highest first (categorical descriptive analysis).

For food effect cohort, an adverse event starting in one period and continuing into the next period is counted only in the onset period.

Assigned treatment	Definition
Treatment Period 1 (Fasting)	AE start date/time is on or after the dose date/time of treatment received in Period 1 and prior to the date/time of treatment received in period 2 (fed period) no matter when AE stops.
Treatment Period 2 (Fed)	AE start date/time is on or after the dose date/time of treatment received in Period 2 until the end of study.

For Part 1 (SAD) Cohort S3 food effect arm, TEAE will be further assigned to S3/Fasted (period 1) or S3/Fed (period 2) by using period 2 start date and TEAE's that start post first study drug administration of period 2 (Fed) will not be attributed to treatment during period 1 (Fasted). TEAE's that start post first study drug administration of period 1, but prior to first study drug administration of period 2, will be attributed to period 1 only. TEAEs that start post first study drug administration of period 1 (Fasted) and ongoing will be attributed to Onset period only

The TEAE summaries will include:

- Overall summary of TEAEs.
- TEAE summary by SOC and PT.
- TEAE summary of serious events by SOC and PT.
- TEAE summary by SOC, PT and Severity.
- TEAE summary by SOC, PT and relationship to study drug.
- TEAE summary of events leading to the study drug discontinuation by SOC and PT.
- Overall Frequency of TEAE by PT.
- Overall Frequency of related TEAE by PT.

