If a participant has multiple occurrences of a concomitant medication, the participant is presented only once in the participant count (n) column for a given ATC and PT. Occurrences are counted each time in the mentions/occurrence (m) column.

Percentages are calculated (the denominator used for the calculation) based on the number of participants in the safety population in each treatment group (N).

World Health Organization-Drug Dictionary (WHO-DD) Version xx, YYYY

Programing Note:

Add following treatment columns;
 CVN766 5 mg, CVN766 15 mg, CVN766 45 mg(Fasted), CVN766 45 mg(Fed) CVN766 125 mg, CVN766 250 mg, Overall CVN766, Overall Placebo, Placebo (Fed) and Overall
 Overall CVN766 will not contain CVN766 45 mg(Fed)
 Overall Placebo will not contain Placebo (Fed) from S3 Cohort.

Table 14.3.2.2 Summary of Concomitant Medications MAD (Safety Population)

Programing Note:
Same as Table 14.3.1.1
Source: Listing 16.2.10.2.2
Add following treatment columns;
CVN766 45 mg, CVN766 125 mg, CVN766 250 mg, Overall CVN766, Overall Placebo and Overall.

Table 14.3.3.1.1 Summary of Overall Treatment Emergent Adverse Events SAD (Safety Population)

	CVN766 5 mg (N=xx) n (%) m	etc.	Overall (N=xx) n (%) m
Number of Participants Reporting at least one:			
TEAE	xx (xx.x%) xx	xx (xx.x%) xx	xx (xx.x%) xx
Severe TEAE	xx (xx.x%) xx	xx (xx.x%) xx	xx (xx.x%) xx
Treatment Related TEAE	xx (xx.x%) xx	xx (xx.x%) xx	xx (xx.x%) xx
Serious TEAE	xx (xx.x%) xx	xx (xx.x%) xx	xx (xx.x%) xx
TEAE leading to study drug withdrawal[1]	xx (xx.x%) xx	xx (xx.x%) xx	xx (xx.x%) xx
TEAE leading to discontinuation from study	xx (xx.x%) xx	xx (xx.x%) xx	xx (xx.x%) xx
Life threatening TEAE	xx (xx.x%) xx	xx (xx.x%) xx	xx (xx.x%) xx
TEAE leading to death	xx (xx.x%) xx	xx (xx.x%) xx	xx (xx.x%) xx

Source: Listing 16.2.7.1.1

Treatment Emergent Adverse Events (TEAEs) are defined as adverse events that occurred following the first administration of study medication. If a participant has multiple occurrences of a TEAE, the participant is presented only once in the Participant count (n) column for a given System Organ Class and Preferred Term. Occurrences are counted each time in the mentions/Occurrence (m) column.

Percentages are calculated (the denominator used for the calculation) based on the number of participants in the safety population in each treatment group (N).

[1]Action taken = drug withdrawn

Medical Dictionary for Regulatory Activities (MedDRA) Version xx.x

Programing Note:

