Listing 16.2.6.6.1 CV Telemetry SAD (Pharmacokinetic Population)

Treatment: CVN766 5 mg

Test: CV Telemetry

Subject ID	Visit	Time Point	Were CV Telemetry performed? if No-reason	Start Date/time of Monitoring (YYYY-MM-DD/HH:MM)	End Date/time of Monitoring (YYYY-MM-DD/HH:MM)	Assessment Value	Abnormality Description
XXX	Screening		Yes	YYYY-MM-DD/ HH:MM	YYYY-MM-DD/ HH:MM	Normal	
	Day -1			YYYY-MM-DD/ HH:MM	YYYY-MM-DD/ HH:MM	Abnormal CS	xxxx
	Day 1	4 hours post-dose	Yes	YYYY-MM-DD/ HH:MM	YYYY-MM-DD/ HH:MM	xx	
		8 hours post-dose	Yes	YYYY-MM-DD/ HH:MM	YYYY-MM-DD/ HH:MM	xx	
	Day 2	24 hours post-dose	Yes	YYYY-MM-DD/ HH:MM	YYYY-MM-DD/ HH:MM	xx	
...							

N/A = Not Applicable.

Programing Note:
 Add following treatment columns;
 CVN766 5 mg, CVN766 15 mg, CVN766 45 mg (Fasted), CVN766 45 mg (Fed), CVN766 125 mg, CVN766 250 mg.

Listing 16.2.7.1.1 Adverse Events SAD (Safety Population)

Treatment CVN766 5 mg

Subject ID	Adverse Event Verbatim/ System Organ Class/ Preferred Term	Start Date/ Time/ (YYYY-MM-DD/ HH:MM)	End Date/ Time/ (YYYY-MM-DD/ HH:MM)	Pre-treatment event?	Severity	SAE/ Reason	Relationship to Study Treatment	Action Taken	Concomitant Medication/ Other Action	Outcome	Subject Discontinued due to AE	TEAE
XXX	XXXXXXXXXXXXXXXXXXXX ZZZZZZZZZZZZZZZZZZZZ YYYYYYYYYYYYYYYYYYYY	YYYY-MM-DD HH:MM	YYYY-MM-DD HH:MM	No	Mild	Yes/Death	Related	N/A	Yes, CM1/No	Recovered/ Resolved	No	Yes
XXX	XXXXXXXXXXXXXXXXXXXX ZZZZZZZZZZZZZZZZZZZZ YYYYYYYYYYYYYYYYYYYY	YYYY-MM-DD HH:MM	YYYY-MM-DD HH:MM		Mild	Yes/hospitalization	Unrelated	Dose not changed	No/ Yes, CM1/No	Recovering / Resolving	No	Yes
...												

SAE = Serious Adverse Event. TEAE = A treatment-emergent adverse event.

Medical Dictionary for Regulatory Activities (MedDRA) Version xx.x

Programming Note:

Add following treatment columns;
 CVN766 5 mg, CVN766 15 mg, CVN766 45 mg(Fasted), CVN766 45 mg(Fed), CVN766 125 mg, CVN766 250 mg.

Listing 16.2.7.1.2 Adverse Events MAD (Safety Population)

Programming Note:

Same as Listing 16.2.7.1.1
 Add following treatment columns;
 CVN766 45 mg, CVN766 125 mg, CVN766 250 mg.

Listing 16.2.7.2.1 Serious Adverse Events SAD (Safety Population)

Treatment: CVN766 5 mg
 SAE Reason: Hospitalization

Subject ID	Adverse Event Verbatim/ System Organ Class/ Preferred Term	Start Date/ Time/ (YYYY-MM-DD/ HH:MM)	End Date/ Time/ (YYYY-MM-DD)	Severity	SAE/ Reason	Relationship to Study Treatment	Action Taken	Concomitant Medication/ Other Action	Outcome	Subject Discontinued due to AE	TEAE

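### The TEAE definition has no clause for worsening, so an AE present before the first dose that worsens after it is left out of the primary TEAE percentage unless the worsening is recorded as a new AE

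*SAP*

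**What the plan says.** The first primary endpoint in SAP section 2.3 is "Percentage of subjects who experience at least one treatment-emergent adverse event (TEAE").

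The TEAE rule appears in two forms:

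- Section 3.2: TEAEs "are defined as adverse events that occurred within 30 days", with the window computed as "onset date – last date of dose + 1 ≤ 30) after study drug administration".
- Mock Table 14.3.3.1.1, with the sentence repeated under the other SAD TEAE tables, to which the MAD shells refer back: "Treatment Emergent Adverse Events (TEAEs) are defined as adverse events that occurred following the first administration of study medication".

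Section 11.1 adds "All AE summaries will be restricted to TEAEs only". For the food-effect cohort it says that "an adverse event starting in one period and continuing into the next period is counted only in the onset period", and it assigns an event to Period 2 (Fed) when the "AE start date/time is on or after the dose date/time of treatment received in Period 2 until the end of study".

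Section 3.5 classifies events with missing or partial dates. Mock Listing 16.2.7.1.1 has a column headed "Pre-treatment event" and shows one start, one end and one severity per row. None of these places mentions an event that is already present when a dose is given and gets worse afterwards.

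**The concern.** A worsening after dosing of something that was there before is a possible drug effect. A TEAE definition usually captures it, because the purpose of the category is to gather what emerged or increased under treatment. Here the definition rests on when the event began.

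Take a mild headache noted at check-in on Day -1 that becomes severe after the dose. If the site keeps it as one AE, its onset is before dosing and it is not a TEAE. Because only TEAEs are summarised, it is then absent from all eight TEAE summaries listed in section 11.1, including those by severity, seriousness, relationship and discontinuation, and it remains only in a listing.

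With six active subjects per cohort, one classification decision can visibly move a primary result. In S3 a related question arises at the second dose: an event that began after the fasted dose and intensified after the fed dose has a single onset, so it is shown under Fasted alone.

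**Working it through.** The SAP gives no figure for the definition itself, so the check is of wording first and denominators second.

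**1. Does any rule admit a pre-dose event that worsens?**

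| Place in SAP | Decides on | Worsening clause |
|---|---|---|
| Section 3.2 | onset date relative to last dose, 30-day limit | none |
| TEAE table footnotes | having occurred after first dose, no upper limit | none |
| Section 3.5, missing or partial dates | start date, or an end date before first dose; all dates missing counts as TEAE | none |
| Section 11.1, S3 periods | start date/time against the Period 1 and Period 2 doses | none |

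The bracketed expression in section 3.2 has no lower bound. Onset three days before dosing gives -3 + 1 = -2, and onset on the dosing day gives 0 + 1 = 1; both are at most 30. Pre-dose onset is excluded only by the words that place the event after study drug administration. The footnotes and the pre-treatment column of Listing 16.2.7.1.1 agree with that reading. A fully dated pre-dose event is therefore not a TEAE, and no rule brings it back if it worsens.

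**2. How does the recording convention change this?**

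- Worsening entered as a new AE with its own start date: the start is after the dose, so it is a TEAE (and Fed in S3 if it starts on or after the Period 2 dose). The loss is zero.
- Worsening kept in the same AE: onset stays before the dose, and the event is left out.

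Listing 16.2.7.1.1 fits either convention. It shows no date of severity change. The SAP does not say which applies.

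**3. Denominators.** Sections 2.1 and 2.4 give five SAD cohorts and three MAD cohorts of 8, split 6 active to 2 placebo. Total: 5 × 8 + 3 × 8 = 64, which reproduces the stated sample size. The optional cohort S3a is not included in what follows.

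**4. Effect of one affected subject with no other TEAE**, as 100/N percentage points:

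| Column | N | Shift (points) |
|---|---|---|
| Any dose level, active | 6 | 16.7 |
| SAD Overall CVN766 | 5 × 6 = 30 | 3.3 |
| SAD Overall Placebo | 5 × 2 = 10 | 10.0 |
| MAD Overall CVN766 | 3 × 6 = 18 | 5.6 |
| MAD Overall Placebo | 3 × 2 = 6 | 16.7 |

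If the subject has another TEAE, the shift in the primary percentage is zero, and only the severity, seriousness and preferred-term tables are affected. The documents give no rate for such events, so no expected bias can be computed.

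**5. S3.** An event that starts after the fasted dose is already a TEAE under Fasted. Section 3.7 includes Fasted and excludes Fed from Overall CVN766, so the subject stays in the pooled count. What can be wrong is the Fed column (one of six active subjects, 16.7 points, if that subject has no other Fed TEAE) and the period against which the higher severity is shown.

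**The case against.** The strongest objection is that the loss depends on how AEs are recorded, and that convention often sits in the protocol or CRF guidance, which are not at hand. If a worsening opens a new AE, nothing is lost. This stands as a condition on the size of the problem. It does not remove the gap, because the SAP fixes the TEAE rule itself and does not say that it relies on such recording.

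Several further points stand:

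- The footnote speaks of events that occurred, which is looser than started. The onset reading rests mainly on sections 3.2 and 11.1.
- The missing-date rules in section 3.5 use end dates too and lean towards inclusion, so it would be wrong to say that every rule in the SAP turns on onset alone.
- The events stay visible in the AE listings; laboratory, vital-sign and ECG values are also summarised as change from baseline. The analysis is descriptive, so no hypothesis test is altered.
- Subjects are healthy volunteers, so AEs ongoing at dosing may be few.

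A reader might infer that in S3 an effect of the fed dose is charged to the fasted dose. The documents do not support that as stated. Onset-period attribution is a deliberate convention, applied consistently in section 11.1 and in section 9 for concomitant medications. The event would have to last across a gap of at least 14 days and then intensify, and intensifying after the fed dose does not show that the fed dose caused it. Nor do the shells show that a later severity overwrites an earlier one.

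**Conclusion.** The point holds in a limited, conditional form. As written, an AE present before the first dose that becomes more severe or serious afterwards is outside the TEAE definition, and so outside the first primary endpoint and every AE table, unless the worsening has its own AE record. One such subject without another TEAE moves the percentage by 16.7 points at a dose level, 5.6 points in MAD pooled active and 3.3 points in SAD pooled active.

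This rests on three assumptions: pre-dose onset is excluded, as the words of section 3.2 indicate; the worsening is not entered as a new AE; and cohorts are filled as planned. How many subjects would be affected is unknown and may be none.

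It should not be read as showing that events have been lost, or that S3 subjects drop out of the TEAE count. In S3 the gap concerns only the period and severity under which a worsening is shown.

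**What to change.** Use one definition in section 3.2, section 11.1 and all TEAE footnotes: an AE that starts on or after the first dose, or that starts earlier and increases in severity or becomes serious on or after the first dose, within the stated window. Using the same text throughout also removes the present difference between section 3.2, which has a 30-day limit, and the footnotes, which have none.

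State the data source: a worsening is taken from a separate AE record, or from a dated change in severity or seriousness, and the worsening date serves as its start date.

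For S3, keep onset-period attribution for ongoing events that do not change. Assign a worsening dated on or after the Period 2 dose to Fed at its new severity, and leave the earlier severity under Fasted.

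If worsening is already recorded as a new AE in this study, one sentence saying so in section 3.2, together with the common definition, is enough.

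The cost is SAP wording and a short derivation, provided the worsening date exists in the AE data. The listing shells show no such field, and the mock shells carry a data cut-off of 2022-10-26, so availability must be checked first; without separate records or dated changes the derivation cannot be done. TEAE percentages may become slightly less favourable.

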11.3 Vital Signs

The following vital signs measurements will be taken at the time points specified in the Schedule of Events (refer to the Protocol):

- Pulse (beats/min);
- Systolic Blood Pressure (SBP) (mmHg)
- Diastolic Blood Pressure (DBP) (mmHg)
- Respiratory Rate (breaths/min)
- Body Temperature (°C)

All vital signs data collected at scheduled and unscheduled visits will be included in the listings, but only results collected as scheduled visits will be included in the summary tables.

Triplicate orthostatic vital signs (blood pressure and heart rate) will be recorded at baseline (Check-in Day -1) 15 minutes apart (the average will be used to determine eligibility).

The parameter names that will be used in the outputs will comprise of the test name and the unit of measure, for example, 'Systolic Blood Pressure (mmHg)'. Parameters will be sorted in the order that the measurements were collected in on the Vital Signs eCRF page within the tables and listings.

Vital signs measurements will present summary statistics for the results at the baseline and each scheduled post-baseline visit for each of the parameters in Supine and Standing position. In addition, summaries will be presented for the change from baseline values at each scheduled post-baseline visit in Supine and Standing position (continuous descriptive analysis). The average of triplicate vital signs in Supine and Standing position will be used as baseline for HR and BP.

In addition, vital signs and postural changes, the individual subject level at each time point between the two positions in which readings are taken (Supine vs Standing) will be reported. At each timepoint standard descriptive stats for HR, sBP and dBP postural data will be reported.

Further, a categorical tabulation for number (percentage) of subjects per time point (and overall categories for any post-exposure timepoint for each parameter separately and for the 2 BP measures together) for the following clinically changes will be created:

- Drop in dBP of ≥ 10 mmHg when moving from supine to standing
- Drop in sBP of ≥ 20 mmHg when moving from supine to standing
- Increase in HR of ≥ 30 bpm when moving from supine to standing

The decimal precision to which the summaries for each parameter will presented will be based on the maximum number of decimals to which the results were reported on the eCRF.

11.4 12-Lead Electrocardiogram (ECG)

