Table 14.3.5.1.2 Summary of Vital Signs MAD (Safety Population)

Programing Note:
Same as Table 14.3.5.1.1
Source: Listing 16.2.9.1.2
Add following treatment columns;
CVN766 45 mg, CVN766 125 mg, CVN766 250 mg, Overall CVN766, Overall Placebo and Overall.
Repeat for Position: Supine, Standing

Table 14.3.5.2.1 Summary of Orthostatic Vital Signs SAD (Safety Population)

Parameter: Heart rate (beats/min)

Treatment	Visit	Timepoint	Orthostatic Change					
			n	Mean	SD	Median	Minimum	Maximum
CVN766 5 mg (N=xx)	Baseline[1]		xx	xx.x	xx.x	xx.x	xx	xx
	Day 1	0.5 hours	xx	xx.x	xx.x	xx.x	xx	xx
		1 hours	xx	xx.x	xx.x	xx.x	xx	xx
		2 hours	xx	xx.x	xx.x	xx.x	xx	xx
		4 hours	xx	xx.x	xx.x	xx.x	xx	xx
		8 hours	xx	xx.x	xx.x	xx.x	xx	xx
		12 hours	xx	xx.x	xx.x	xx.x	xx	xx
	Day 2	24 hours	xx	xx.x	xx.x	xx.x	xx	xx
		36 hours	xx	xx.x	xx.x	xx.x	xx	xx
	Day 3	48 hours	xx	xx.x	xx.x	xx.x	xx	xx
		60 hours	xx	xx.x	xx.x	xx.x	xx	xx
	Day 4	72 hours	xx	xx.x	xx.x	xx.x	xx	xx
	Day 8		xx	xx.x	xx.x	xx.x	xx	xx
	ET		xx	xx.x	xx.x	xx.x	xx	xx
...						

Source: Listing 16.2.9.1.1

[1] Baseline is defined as the last available, valid, non-missing observation prior to first study drug administration.

N/A = Not Applicable. SD = Standard Deviation.

ET = Early Termination.

Orthostatic Change = value of parameter in standing - value of parameter in supine.

Programming Note:

Add following treatment columns;

CVN766 5 mg, CVN766 15 mg, CVN766 45 mg(Fasted), CVN766 45 mg(Fed), CVN766 125 mg, CVN766 250 mg, Overall CVN766, Overall Placebo Placebo(Fed) and Overall

Overall CVN766 will not contain CVN766 45 mg(Fed)

Overall Placebo will not contain Placebo (fed) from S3 cohort

Table 14.3.5.2.2 Summary of Orthostatic Vital Signs MAD (Safety Population)

Parameter: Heart rate (beats/min)

Treatment	Visit	Timepoint	Orthostatic Change					
			n	Mean	SD	Median	Minimum	Maximum
CVN766 45 mg (N=xx)	Baseline[1]		xx	xx.x	xx.x	xx.x	xx	xx
	Day 1	0.5 hours	xx	xx.x	xx.x	xx.x	xx	xx
		1 hours	xx	xx.x	xx.x	xx.x	xx	xx
		2 hours	xx	xx.x	xx.x	xx.x	xx	xx
		4 hours	xx	xx.x	xx.x	xx.x	xx	xx
		8 hours	xx	xx.x	xx.x	xx.x	xx	xx
		12 hours	xx	xx.x	xx.x	xx.x	xx	xx
	Day 2	24 hours	xx	xx.x	xx.x	xx.x	xx	xx
		36 hours	xx	xx.x	xx.x	xx.x	xx	xx
	Day 3	48 hours	xx	xx.x	xx.x	xx.x	xx	xx
		60 hours	xx	xx.x	xx.x	xx.x	xx	xx
	Day 4	72 hours	xx	xx.x	xx.x	xx.x	xx	xx
	Day 8		xx	xx.x	xx.x	xx.x	xx	xx
	ET		xx	xx.x	xx.x	xx.x	xx	xx
...						

Source: Listing 16.2.9.1.1

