 [1] Baseline is defined as the last available, valid, non-missing observation prior to first study drug administration.
 N/A = Not Applicable. SD = Standard Deviation.
 ET = Early Termination.
 Orthostatic Change = value of parameter in standing - value of parameter in supine.

Programming Note:
 CVN766 45 mg, CVN766 125 mg, CVN766 250 mg, Overall CVN766, Overall Placebo and Overall.

Table 14.3.5.3.1 Summary of Categorical analysis of Orthostatic Vital Signs SAD (Safety Population)

Category: Drop in dBP of ≥ 10 mmHg from Supine to Standing

Visit	Timepoint	TRTA N=xxx n (%)	TRTB N=xxx n (%)	TRTC N=xxx n (%)	...
Day 1	0.5 hours	xx	xx	xx	xx
	1 hours	xx	xx	xx	xx
	2 hours	xx	xx	xx	xx
	4 hours	xx	xx	xx	xx
	8 hours	xx	xx	xx	xx
	12 hours	xx	xx	xx	xx
	24 hours	xx	xx	xx	xx
	36 hours	xx	xx	xx	xx
	48 hours	xx	xx	xx	xx
	60 hours	xx	xx	xx	xx
	72 hours	xx	xx	xx	xx
...					

Source: Listing 16.2.9.1.1

Programing Note:

Add following treatment columns;

CVN766 5 mg, CVN766 15 mg, CVN766 45 mg(Fasted), CVN766 45 mg(Fed), CVN766 125 mg, CVN766 250 mg, Overall CVN766, Overall Placebo Placebo(Fed) and Overall

Overall CVN766 will not contain CVN766 45 mg(Fed)

Overall Placebo will not contain Placebo (Fed) from S3 Cohort

Repeat for Category: Drop in dBP of ≥ 10 mmHg from Supine to Standing, Drop in sBP of ≥ 20 mmHg when moving from supine to standing, Increase in HR of ≥ 30 bpm when moving from supine to standing

Table 14.3.5.3.2 Summary of Categorical analysis of Orthostatic Vital Signs MAD (Safety Population)

Category: Drop in dBP of ≥ 10 mmHg from Supine to Standing

Visit	Timepoint	TRTA N=xxx n (%)	TRTB N=xxx n (%)	TRTC N=xxx n (%)	...
Day 1	0.5 hours	xx	xx	xx	xx
	1 hours	xx	xx	xx	xx
	2 hours	xx	xx	xx	xx
	4 hours	xx	xx	xx	xx
	8 hours	xx	xx	xx	xx
	12 hours	xx	xx	xx	xx
	24 hours	xx	xx	xx	xx
	36 hours	xx	xx	xx	xx
	48 hours	xx	xx	xx	xx
	60 hours	xx	xx	xx	xx
	72 hours	xx	xx	xx	xx
...					

Source: Listing 16.2.9.1.2

Programing Note:

CVN766 45 mg, CVN766 125 mg, CVN766 250 mg, Overall CVN766, Overall Placebo and Overall.
 Repeat for Category: Drop in dBP of ≥ 10 mmHg from Supine to Standing, Drop in sBP of ≥ 20 mmHg when moving from supine to standing, Increase in HR of ≥ 30 bpm when moving from supine to standing

Table 14.3.5.4.1.1 Summary of 12-Lead ECG SAD (Safety Population)

Parameter: Heart Rate (bpm)

Treatment	Visit	Timepoint	Actual Value						Change from Baseline[1]					
			n	Mean	SD	Median	Minimum	Maximum	n	Mean	SD	Median	Minimum	Maximum

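### The categorical orthostatic shells omit summaries that SAP section 11.3 requires, and with no baseline row they cannot separate pre-existing from new postural changes

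*SAP*

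**What the plan says.** Section 11.3 of the SAP sets up both the baseline data and the responder analysis. On the data: "Triplicate orthostatic vital signs (blood pressure and heart rate) will be recorded at baseline (Check-in Day -1) 15 minutes apart". The parenthesis that follows adds that "the average will be used to determine eligibility". Later in the section: "The average of triplicate vital signs in Supine and Standing position will be used as baseline for HR and BP". Section 12 repeats that the Day -1 average is the value to use.

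The responder analysis has three criteria: "Drop in dBP of ≥ 10 mmHg when moving from supine to standing", a systolic fall of at least 20 mmHg, and a heart rate rise of at least 30 bpm. Subjects are to be counted at each time point. Section 11.3 also asks for "overall categories for any post-exposure timepoint for each parameter separately and for the 2 BP measures together".

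The mock shells are "Table 14.3.5.3.1 Summary of Categorical analysis of Orthostatic Vital Signs SAD (Safety Population" and "Table 14.3.5.3.2 Summary of Categorical analysis of Orthostatic Vital Signs MAD (Safety Population". Each has eleven rows, Day 1 at 0.5 hours through 72 hours, followed by an ellipsis. Each carries a programming note to repeat the layout for the three criteria one at a time.

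The neighbouring continuous shells, Tables 14.3.5.2.1 and 14.3.5.2.2, do have a Baseline row. They define the quantity shown as "Orthostatic Change = value of parameter in standing - value of parameter in supine".

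**The concern.** There are two separate defects.

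First, the shells do not deliver what the text requires. A programmer working from them would produce three sets of per-time-point counts and stop there. The overall category and the joint systolic/diastolic category would be missing. The overall category is the summary a safety reader looks at first.

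Second, neither the criteria nor the table layout refers to the subject's state before dosing. Some healthy people meet such a threshold on standing without any drug. If one of them does so again after dosing, the table counts that subject exactly as it counts someone whose postural change first appeared on treatment. In the SAP's table list these are the only tables that apply the thresholds. With six active subjects per dose, one such subject can create or mask an apparent dose pattern.

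**Working it through.** The SAP states no figure here to reproduce: section 2.4 says there is no formal sample size calculation. The check sets text against shells, then works out the weight of one subject.

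**Text against shells**

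| Item | Section 11.3 | Shells 14.3.5.3.1 and 14.3.5.3.2 |
|---|---|---|
| Counts at each time point | Required | Present, 11 post-dose rows |
| Overall count, any post-exposure time | Required | No row shown |
| Systolic and diastolic combined | Required | Not in the list of criteria to repeat |
| Baseline status | Baseline defined, but no categorical display requested | No row shown |

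The ellipsis comes after the 72-hour row, so it reads as later visits, not as a baseline row. It cannot supply the combined category, because the programming note names the three criteria explicitly.

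**Against the SAP's other shells**

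Baseline rows appear in the continuous orthostatic shells (14.3.5.2.1, 14.3.5.2.2), the urinalysis shells (14.3.4.3.1, 14.3.4.3.2) and the ECG interpretation shell (14.3.5.4.2.1, which the MAD version follows). The laboratory shift shells cross-classify each post-dose result by baseline category. The categorical orthostatic shells are the exception.

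**Weight of one subject**

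Inputs from section 2.5: 6 active and 2 placebo subjects per cohort, five SAD cohorts, three MAD cohorts.

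- Any one dose column: 1/6 = 16.7%. Two subjects: 2/6 = 33.3%.
- Pooled SAD placebo: 5 × 2 = 10 subjects, so 1/10 = 10.0%.
- Pooled MAD placebo: 3 × 2 = 6 subjects, so 1/6 = 16.7%.

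**How often a recurring drop is counted**

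Suppose a subject who met a criterion before dosing meets it again at each post-dose reading with probability r, independently over the 11 rows. The SAP gives no value for r, so 0.3 to 0.9 is an assumed range.

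- Expected contribution to a single row of a dose column: r/6, which is 0.3/6 = 5.0 points to 0.9/6 = 15.0 points.
- Expected contribution to an any-post-dose row: [1 − (1 − r)^11]/6. For r = 0.3 this is (1 − 0.7^11)/6 = 0.980/6 = 16.3 points. For r = 0.9 it is 16.7 points.

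So over this range the any-post-exposure summary required by section 11.3 almost always includes such a subject. Baseline status therefore matters most in that row.

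**The case against.** The strongest case against is that section 11.3 never asks for a categorical baseline or a new-onset count, so omitting the Baseline row breaks no rule of the plan. Baseline information also exists elsewhere. Tables 14.3.5.2.1 and 14.3.5.2.2 give the minimum and maximum orthostatic change at baseline. The vital signs listing shows Screening, Day -1 and pre-dose values in both positions. Section 11.3 says that supine-to-standing changes will be reported for individual subjects. The placebo columns carry the same background rate in expectation. The Day -1 average also feeds eligibility, so habitual responders might have been excluded.

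Much of this limits the size of the point but does not remove it. A minimum or maximum can show that someone crossed a threshold at baseline. It does not show how many did, or whether the same subjects crossed it later. The listing shell has no postural-difference column and no criterion flag, so a reader would have to subtract by hand. Placebo columns of 6 to 10 subjects cannot be relied on to balance a few habitual responders. The SAP does not give the eligibility limits, so whether they exclude such subjects cannot be told from this document.

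Three stronger readings should be resisted:

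- A reader might infer that drops seen before dosing are themselves counted as post-dose findings. They are not: every row shown holds post-dose readings, and a subject is counted only if a criterion is met again.
- A reader might infer that such a subject appears in every row. That assumes perfect recurrence, which nothing in the SAP supports.
- A reader might measure the defect by the chance of at least one hit over 11 readings. With an assumed background rate q of 2% to 10% per reading and independence, 1 − (1 − q)^11 is 19.9% to 68.6%. That measures repeated readings, not missing baseline status. Excluding subjects who met the criterion at a single baseline reading would leave (1 − q)[1 − (1 − q)^11], which is 0.98 × 0.199 = 19.5% to 0.90 × 0.686 = 61.7%. Most of the figure would remain.

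**Conclusion.** The point holds as a minor one. The conflict between section 11.3 and the two shells is a matter of record: the overall any-post-exposure row and the combined blood pressure category are required by the text and not shown in the shells. The missing Baseline row departs from the SAP's own pattern. It leaves the tables unable to say how many post-dose cases already met the criterion before dosing.

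The size is 16.7 points in a dose column for each recurring subject. Against pooled placebo the weight is unequal only in SAD (10.0 points); in MAD it is the same 16.7 points. These figures assume full planned cohorts of 6 active and 2 placebo. How many such subjects will enrol is unknown. Because the tables are descriptive, the harm is to how a safety table is read, not to any test or estimate.

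**What to change.** In both Table 14.3.5.3.1 and Table 14.3.5.3.2:

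- Add the any-post-exposure row for each criterion and the combined systolic/diastolic category, as section 11.3 already requires.
- Add a Baseline row applying the same criteria to the averaged Day -1 supine and standing values.
- Add a row counting subjects who met the criterion at any post-dose time but not at baseline.
- Add a footnote defining this baseline. It is needed because section 3.2 and the footnotes to the other vital signs shells use the last observation before first dosing, and the vital signs listing shell marks the Day 1 pre-dose reading as baseline.

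The cost is a few rows from data already collected. There is one small downside. An average of three readings varies less than a single reading, and the SAP does not say that post-dose values are averaged. Some subjects near a threshold may therefore miss it at baseline and meet it later by chance, making the new-onset count somewhat high. The footnote should say so.
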